4.4 Purpose and timing of interim analyses/design adaptations

An interim assessment (IA) will be performed after completion of Cohort 2. The study team and an independent DMC will review key PK/efficacy/safety data including the proportion of participants with $\geq 90\%$ parasite reduction at 12 hours as well as at 24 and 48 hours and parasite reduction ratios, relevant safety data and PK data from all participants of Cohorts 1 and 2. Based on data from Cohorts 1 and 2, the highest safe and effective exposure will be determined and used to select doses for Cohorts 3-5.

For subsequent Cohorts 3-5, randomization will start with the next descending age group. Novartis pharmacokineticist will review the PK exposure and AAG (if required) in up to 6 participants treated with IV cipargamin. After confirming that the exposures are adequate,

enrollment of participants will continue in the initial cohort (applicable for Cohorts 3-5) and the next lower age cohort will be opened for enrollment. However, enrollment for Cohort 5 will only be initiated post completion of Cohort 4 and a DMC meeting. In case, the dose for a specific age group has to be adjusted, additional participants with the modified dose may be recruited.

Additional IAs may be conducted (for e.g. after Cohort 4) to support decision making concerning the current clinical study, the sponsor's clinical development projects in general, or in case of any safety concerns.

Following dose and design adaptations are permitted in the study as per below [Table 4-1](#):

Table 4-1 Dose and design adaptations permitted in the study

For Cohorts 1-2, CCI	-	Cohort 1	Cohort 2	Interim assessment to identify safe and efficacious exposure range (CCI) for Cohorts 3-5	Cohort 3-5
	Doses	20 mg and 40 mg May be modified before start of study based on IV cipargamin PK data from FIH study	20 mg and 40 mg May be modified based on emerging PK data from Cohort 1 or if one of the IV cipargamin treatment arms meets the stopping criteria		Age and weight band based dose may be modified based on PK data from up to first 6 participants in each of the cohort to achieve adequate exposure identified for Cohorts 3-5

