6.2 Other treatment(s)

6.2.1 Rescue medication

Management of severe malaria consists of an IV antimalarial (cipargamin or artesunate in the study) followed by a full course of oral standard of care (Coartem in this study). Hence, rescue medication use will also be either IV medication or oral medication as applicable.

Participants randomized to IV artesunate will not be administered any other IV antimalarial as rescue medication since IV artesunate is the only standard of care. Participants randomized to IV cipargamin may be rescued with IV artesunate, if they meet the following pre-defined criteria:

- Parasite clearance < 90% at 24 hours post treatment initiation
- Clinical decline of severe malaria symptoms (per Investigator) at any time
- Participants not able to take oral antimalarial along with presence of parasites at 72 hour post treatment initiation
- Participants developing signs or symptoms of severe malaria after shift to oral standard of care (Coartem) until end of the study (Day 29).

In addition, participants developing safety concerns due to cipargamin (Refer also [Section 16.1](#), [Section 16.2](#)) can be rescued with IV artesunate.

After completion of full course of Coartem, participants meeting the following criteria will be administered another ACT (as per local guidance) as an oral rescue medication:

- Parasitemia at any time with or without temperature > 37.5°C

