Analysis of secondary endpoints related to parasite clearance dynamics

All analyses will be performed using the FAS.

Proportions of participants with ≥ 90% *P. falciparum* asexual parasite reduction from baseline at 24 and 48 hours: missing data due to intercurrent and non-intercurrent events will be handled similar to the primary efficacy endpoint (See [Section 12.4.3](#), [Section 12.4.4](#)). These 2 variables will be analyzed using the statistical methods specified in [Section 12.4.2](#), [Section 12.4.5](#) and [Section 12.4.6](#).

PRRs at 12, 24 and 48 hours: PRR is defined as the ratio of asexual parasite at baseline divided by asexual parasite at post-baseline. If the asexual parasite count at post-baseline is 0, the half value of detection limit will be used to calculate the ratio. Missing values will not be imputed. For each PRR, 2-sided 90% CIs for each treatment group and for treatment ratio between each IV cipargamin regime vs IV artesunate by cohort will be provided using an analysis of covariance (ANCOVA) model on the log scale with log baseline value as a covariate and treatment group as a factor. For all cohorts pooled, the analysis will be performed with cohort as an additional factor in the ANCOVA model.

PCT and FCT: PCT will be calculated based on uncorrected *P. falciparum* asexual parasite counts. If a participant does not experience an event (such as *P. falciparum* parasite clearance, etc.), the time to the event will be censored at the last relevant assessment (such as last *P. falciparum* parasite assessment, etc.) participants who do not have the health condition at baseline (eg, fever, etc.) will be excluded from the corresponding time to event analysis (eg., FCT, etc.). Descriptive statistics will provided using the Kaplan-Meier method and Kaplan-Meier curves will be presented by treatment and cohort. For all cohorts pooled, difference for the cipargamin regimen vs artesunate will be evaluated using a log-rank test stratified by cohort. Two-sided 90% CIs for the hazard ratio will be provided.

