2.7.2.4 Time to event analyses

Time to event will be calculated from the time of first study medication to the date of first event if a patient experiences the event and be censored at the time of last assessment if a patient does not experience the event. Randomization date will be used in the absence of study medication date.

For the following time to event variables, the first visit with the event will be used to calculate the time if a patient experiences the event. If a patient does not experience the event, the time will be censored at the last visit assessment for the specific type of event (such as last sit assessment, etc.) with the exception of date of discontinuation (or death) for time to oral antimalarial therapy.

- Time to *P. falciparum* asexual parasite clearance (PCT) (in hours)
- Time to fever clearance (FCT) (in hours)
- Time to oral antimalarial therapy (in hours),
- Time to recover prostration (in hours) in patients who are prostrated at baseline

Descriptive statistics (mean, standard error, median, quartiles) will be presented using the Kaplan-Meier method by treatment and cohort. Kaplan-Meier curves will be provided by treatment and cohort. For all cohorts pooled, difference for the cipargamin regimen vs artesunate will be evaluated using a log-rank test stratified by cohort (Cohorts 1 and 2 pooled as one cohort). Two-sided 90% CIs for the hazard ratio will be provided.

PCT will be calculated based on *P. falciparum* asexual parasite counts. Patients without parasite clearance for whatever reason will be censored at the time of last parasite assessment. Patients who received any non-study IV antimalarial medication (including IV rescue medication) before parasite clearance will be censored at the first use of antimalarial medication.

Patients who did not have a fever at pre-dose will not be included in the analysis of FCT. Patients without fever clearance for whatever reason will be censored at the time of last temperature assessment. Patients who received any antimalarial medication (including rescue medication) before fever clearance will be censored at the first use of antimalarial medication.

Patients without switching to oral medication for whatever reason will be censored at the time of last study assessment. Patients who received any IV rescue medication will be censored at the first use of IV rescue medication.

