2.7.2.5 Analyses of secondary endpoints related to parasite clearance dynamics

The following analyses are described for the $\geq 90\%$ *P. falciparum* asexual parasite reduction, PRR and PCE slope half-life. The analysis will be based on FAS.

- Proportions of patients with $\geq 90\%$ *P. falciparum* asexual parasite reduction from baseline at 24 and 48 hours

For these two endpoints, data will be analyzed similar to the analysis of primary endpoint as specified in [section 2.5.2](#). Intercurrent events as well as missing data will also be handled similar to that of primary endpoint as specified in [section 2.5.3](#) and [section 2.5.4](#).

- *P. falciparum* asexual parasite reduction ratios (PRR) at 12, 24 and 48 hours

For each patient, the asexual PRR at a specific timepoint will be calculated as the ratio of asexual parasite at baseline divided by asexual parasite at that timepoint. If the asexual parasite count at a timepoint is 0/below assay detection limit, the detection limit will be used to calculate the ratio.

Descriptive statistics including median and geometric mean of asexual PRR at Hour 12, 24 and 48 will be provided by cohort and treatment group using the FAS. For each PRR, 2-sided 90% CIs for geometric mean for each treatment group and geometric mean ratio between each IV cipargamin regime vs IV artesunate by cohort will be provided using an analysis of covariance (ANCOVA) model on the log scale with log baseline value as a covariate and treatment group as a factor by assuming PRRs follow log normal distribution and transformed back using the exponential.

For all cohorts pooled, the analysis will be performed with cohort as an additional factor in the ANCOVA model. Observed data will be used.

- PCE slope half-life

Parasite clearance rate constant and slope half-life for parasite clearance will be calculated for each patient using the WWARN (World Wide Antimalarial Resistance Network)

Parasite Clearance Estimator as described in [Flegg et al. \(2011\)](#). The following are the key steps:

For each patient separately:

Step 1: Perform data cleaning. All further steps are performed on data with outliers, tails, extreme values and trailing zeros removed. For convenience of notation, if there is a zero parasitaemia that directly follows the last positive parasitaemia, it is replaced with the detection limit. This data point is subsequently counted as a non-zero parasite count.

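### As written, parasite counts taken after rescue IV artesunate enter the cipargamin arm's PRR (mainly at 48 h) and PCE half-life, although the neighbouring clearance endpoints treat rescue as failure or censor at it

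*SAP*

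**What the plan says.** **PRR at 12, 24 and 48 h.** SAP 2.7.2.5 uses the FAS, which SAP 2.2 analyses by randomized treatment, and fits an ANCOVA on the log scale. The instruction on data is "For all cohorts pooled, the analysis will be performed with cohort as an additional factor in the ANCOVA model. Observed data will be used". Protocol 12.5.1 adds "Missing values will not be imputed". Neither text mentions rescue for this endpoint.

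**PCE slope half-life.** The SAP's first step reads "All further steps are performed on data with outliers, tails, extreme values and trailing zeros removed". Estimability criteria (i) to (iv) and lag-phase check (v) follow. None refers to rescue.

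**Rescue.** Under Protocol 6.2.1, IV rescue is IV artesunate and is available only to cipargamin patients. One trigger is "Parasite clearance < 90% at 24 hours post treatment initiation"; others include clinical decline at any time and safety concerns. Protocol 9.2 keeps rescued patients in follow-up to Day 29, so post-rescue counts will exist.

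**Neighbouring endpoints.** For ≥90% reduction at 24 and 48 h, SAP 2.7.2.5 says "Intercurrent events as well as missing data will also be handled similar to that of primary endpoint", which makes rescue a non-response. For parasite clearance time (PCT), SAP 2.7.2.4 says "Patients who received any non-study IV antimalarial medication (including IV rescue medication) before parasite clearance will be censored at the first use" of the drug.

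**Use.** PRR is among the interim data in Protocol 4.4 ("as well as at 24 and 48 hours and parasite reduction ratios"). SAP Table 2-13 lists it for the interim assessment after Cohort 2, and again if the review after Cohort 4 is upgraded to an interim analysis.

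**The concern.** PRR and PCE half-life are meant to describe how fast the assigned drug clears parasites. In a rescued cipargamin patient, counts after rescue reflect artesunate on top of residual cipargamin. The parasite-based trigger selects slow clearers, and the artesunate arm has no matching crossover. The contamination is therefore one-sided and concentrated in the patients on whom cipargamin worked least.

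One such patient could be a failure for ≥90% reduction at 48 h, censored for PCT, and credited with artesunate's clearance in PRR48 and half-life. Both affected endpoints are reported with 90% confidence intervals against artesunate. A regimen with more rescues gains more from the rule.

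**Working it through.** The plan states no figure for this effect, so there is none to reproduce. The check has three parts.

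**1. How rescue is handled, endpoint by endpoint**

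| Endpoint | Rule for rescue |
|---|---|
| ≥90% reduction at 24 and 48 h | Non-response (SAP 2.7.2.5, by reference to 2.5.3) |
| PCT | Censored at first non-study IV antimalarial (SAP 2.7.2.4) |
| PRR 12, 24, 48 h | None; "Observed data will be used" |
| PCE half-life | None in the cleaning, estimability or fitting steps |

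The parasite trigger is read from the 24 h count, so it cannot affect PRR12 or PRR24. Those change only if rescue came earlier, for clinical decline or safety. Exposure is mainly PRR48 and PCE.

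**2. Size for PRR48**

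Inputs:
- *b*, artesunate's fall over 24 h: mean PRR24 of 7 to 43 (Protocol 4.2).
- *a*, the fall from 24 to 48 h had cipargamin continued without rescue: not given; assumed 1 (no further fall) to 10.
- *f*, fraction of the arm rescued at 24 h: not given. Illustrated at the largest counts that do not trigger a pause in SAP Table 2-14, where the thresholds are 2 of 14, 6 of 38 and 14 of 116.

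A rescued patient's PRR48 is multiplied by b/a, from 7/10 = 0.7 to 43/1 = 43. The arm's geometric mean is multiplied by (b/a)^f:

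| Rescued | f | Low, 0.7^f | High, 43^f |
|---|---|---|---|
| 1 of 14 | 0.071 | 0.97 | 1.31 |
| 5 of 38 | 0.132 | 0.95 | 1.64 |
| 13 of 116 | 0.112 | 0.96 | 1.52 |

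A factor below 1 needs artesunate to clear more slowly than cipargamin would have done. If cipargamin would have produced a further 10-fold fall, the high end uses 43/10 = 4.3 and becomes 1.11, 1.21 and 1.18. With 1 of 116 rescued and *a* between 2 and 9, the factor is 1.00 to 1.03.

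**3. Size for PCE half-life**

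Half-life = 24 × ln 2 / ln(PRR24). The trigger, PRR24 below 10, means an own half-life above 24 × 0.693 / 2.303 = 7.2 h. Artesunate PRR24 of 43 and 7 correspond to 4.4 h and 8.6 h.

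Illustration, assuming baseline 100,000/µL, detection limit 10/µL, scheduled smear times to 72 h, rescue at 24 h and a log-linear fit. This approximates the PCE tool and is not the tool itself.

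| Own PRR24 | Own half-life | Half-life with post-rescue counts (b = 43 to b = 7) |
|---|---|---|
| 2 | 24.0 h | 6.5 to 11.5 h |
| 5 | 10.3 h | 5.7 to 9.2 h |
| 9 | 7.6 h | 5.8 to 8.1 h |

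In the last row the slower artesunate case lengthens the half-life.

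Rescue can also change who is counted. With own PRR24 = 2 and no rescue, the 72 h count is 100,000/2³ = 12,500/µL, which criterion (iii) (final count ≥1,000/µL) makes non-estimable. With rescue at b = 43 it is 100,000/(2 × 43²) = 27/µL, and the patient becomes estimable with a fast slope. At b = 7 it is 100,000/(2 × 7²) = 1,020/µL, just above the limit, so on counts to 72 h that 11.5 h slope would still not be reported.

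**The case against.** **Different strategies for different endpoints are not an error in themselves.** Analysing all observed counts by randomized arm is a legitimate treatment-policy estimate. That stands in part: the SAP never says that post-rescue counts are to be included. It follows from the observed-data instruction and silence on rescue, and for PCE from silence alone. But no strategy is named, and a treatment-policy PRR48 does not describe cipargamin's own clearance.

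**A reader might infer a very large effect**, for example that a patient at 5,000/µL at 24 h falls to the local detection limit of 10/µL by 48 h, a 500-fold drop. The documents do not support this. Protocol 4.2 gives artesunate PRR24 of 7 to 43, and SAP 5.8.4 expects a median artesunate clearance time above 40 h.

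**A reader might infer that the paediatric dose choice was distorted.** SAP 1.1 records that Cohorts 1 and 2 are complete and that the DMC has endorsed the Cohort 3–4 dosing schedule, so this SAP change cannot alter that choice. Table 2-13 also shows the number of rescued patients beside PRR, and SAP 2.5.5 lists their counts over time, so frequent rescue would be visible.

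**Rescue may be rare.** Protocol 4.2 and SAP 5.8.4 report that most oral-cipargamin patients with uncomplicated malaria cleared by 24 h. Whether this carries over to severe malaria is unknown, but the rescue fractions above are deliberately high. Cipargamin's half-life of about 24 h also means that early post-rescue clearance is mixed, not purely artesunate's.

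**Simply truncating PCE at rescue would create a new bias.** This stands. After a 24 h parasite-triggered rescue, the last usable count exceeds 10% of baseline. For any baseline of at least 10,000/µL that is above 1,000/µL, so criterion (iii) removes the patient. Dropping the slowest clearers would again flatter cipargamin.

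**Conclusion.** The concern holds in a limited form. Applied as written, SAP 2.7.2.5 credits clearance after rescue IV artesunate to cipargamin in PRR48 and PCE half-life, at odds with its handling of the ≥90% endpoints and PCT. PRR12 and PRR24 are touched only by earlier rescue.

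The direction usually favours cipargamin but can reverse slightly. On the assumptions above, geometric-mean PRR48 changes by a factor of about 0.95 to 1.64 at rescue counts just under the pause thresholds, and hardly at all if rescue is rare. The main unknowns are the rescue rate and what cipargamin alone would have done after 24 h; neither is in the documents.

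A reader might take this as a threat to the main conclusion. It is not: the primary endpoint is read at 12 h with rescue counted as failure, and SAP 2.7.2 sets no hypotheses for these secondary endpoints. What is at stake is the final report of clearance speed and any later decision that uses PRR.

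**What to change.** Amend SAP 2.7.2.5 before the final database lock.

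- **PRR.** For timepoints after the first non-assigned antimalarial, in either arm, use the last pre-rescue count in the main analysis. Keep the all-observed analysis as a sensitivity analysis. Because Protocol 12.5.1 plans no imputation for PRR, record the change in SAP section 4, which now lists none. For PRR48 after a 24 h rescue this equals the no-further-fall case (a = 1), so it leans against cipargamin. The gap to the all-observed result would be 7^f to 43^f, for example 1.24 to 1.52 with 13 of 116 rescued.
- **PCE.** Do not fit post-rescue counts as cipargamin clearance. Report by arm how many patients this makes non-estimable under criterion (iii), and add an analysis that ranks them as the slowest clearers. Keep the all-observed fit as a sensitivity analysis.
- **Data.** Take rescue times from the dosing record (DAR) CRF and other antimalarials from the concomitant-medication CRF (SAP 2.4.2). No new collection is needed.

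Cost: SAP wording, a derived flag from two CRFs and one extra rank analysis. PRR48 and half-life may look slightly less favourable for cipargamin, and some slopes will become non-estimable.

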Blood chemistry - Point of Care device, Met Lac Panel	x	x	x	x	x	x
Hematological assessment - Point of Care device	x	x	x	x	x	x
Blood chemistry (INR and/or LDH) at local lab ⁹		x ⁹				
Electrocardiogram (ECG) ¹⁰					x	x
PK Collection ¹²	x	x				
Alpha 1-Acid glycoprotein (AAG) blood collection ¹³						
Urine analysis - local lab	x	x	x	x	x	x
CCI						
CCI						
CCI						
CCI						
CCI						
CCI						
CCI						
Pregnancy Test (serum) ⁷					s	
Body Height						
Body Weight					x	
Administration of IV therapy - Cipargamin (KAE609) Or Artesunate ¹⁸						
Administration of Oral Therapy (standard of care) ²⁰	x ²⁰	x ²⁰				
Contact IRT	x	x	x	x	x	As required
Adverse Events	Ongoing check					
Prior and concomitant medications ²¹	As required					

^x Assessment to be recorded in the clinical database or received electronically from a vendor

^s Assessment to be recorded only in source notes

¹ If participant is eligible for oral therapy and can be discharged per investigator opinion, discharge date will be noted. Earliest timepoint for discharge is 72 H (D4). However if a participant is not eligible to switch to oral therapy and needs to be on IV treatment then extend hospitalization and repeat all D4 assessments every 24 H till the participant is ready to take oral therapy.

² Screening and Randomization visit (D1, 0H) will occur on the same day within 3 hours of screening due to the acute need to treat severe malaria.

³ If participant is eligible for oral therapy then first dose of oral treatment (Coartem) should be given at 48 H (D3), else continue IV therapy.

⁴ D1 - 0 H is randomization visit.

⁵ Prior to start of any study procedure

⁶ Sample to be collected pre-dose

⁷ Pregnancy results must be confirmed negative before dosing. Refer [Section 8.4.6](#).

⁸ Refer modified WHO [Table 16-6](#) in [Section 16.4](#) for detailed assessments.

⁹ INR sample to be collected at pre-dose but only to be analyzed when participant is randomized. Follow-up post baseline samples should only be collected when required as per protocol during elevated lab parameters (refer [Section 16.1](#)) LDH to be collected at pre-dose and D8, and only to be analyzed when hemoglobin is decreased by $\geq 10\%$

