Day of discharge from hospital will be summarized descriptively by cohort and treatment group. Number and percent of patients discharged on different days will be summarized. Day of death will be used in case of death during hospitalization. Time to discharge from hospitalization will also be analyzed using time to event analysis as described in [Section 2.7.2.4](#). Patients who do not discharge or die during study will be censored at the last assessment or at the time of death respectively.

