- for a treatment group in a cohort with 14 patients, the probability of observing at least 2 events is about 80% if the true event rate is $\geq 20\%$ but $< 20\%$ if the true event rate is $\leq 5\%$;
- for a treatment group in a cohort with 20 patients, the probability of observing at least 3 events is about 80% if the true event rate is $\geq 20\%$ but $< 20\%$ if the true event rate is $\leq 7\%$
- for a treatment group in a cohort with 38 patients, the probability of observing at least 6 events is about 80% if the true event rate is $\geq 20\%$ but $< 20\%$ if the true event rate is $\leq 10\%$

- for a regimen that is selected for Cohorts 3-5 with 116 patients, the probability of observing at least 14 events is $> 80\%$ if the true event rate is $\geq 15\%$ but $< 20\%$ if the true event rate is $\leq 9\%$.

The minimal number of events mentioned above may be used as a guidance to interpret the occurrence of safety events in a treatment group in a cohort or pooled cohorts.

Figure 3-3 **Probability of observing selected minimal number of events by sample size**

Generated using R 3.4.3.

4 Change to protocol specified analyses

None

5 Appendix

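### The descriptive day-of-discharge summary enters in-hospital deaths at the day of death, and the SAP censors three recovery-time endpoints at rescue, which only cipargamin patients can receive

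*SAP*

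**What the plan says.** **Discharge.** SAP 2.7.2.5 (analysis of hospitalization data) summarises day of discharge by cohort and treatment, with counts of patients discharged on each day, and adds: "Day of death will be used in case of death during hospitalization". Protocol 12.5.1 has the same sentence. Footnote 1 of Protocol Tables 8-1 and 8-2 puts the earliest discharge at 72 h (Day 4). The same SAP paragraph adds a time-to-event version with a different rule: "Patients who do not discharge or die during study will be censored at the last assessment or at the time of death respectively".

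**Rescue.** SAP 2.7.2.4 says that patients given non-study IV antimalarials, rescue included, "before parasite clearance will be censored at the first use of antimalarial medication". Fever clearance time has a similar rule. For time to oral therapy: "Patients who received any IV rescue medication will be censored at the first use of IV rescue medication". Time to recover from prostration has no such rule, and none is stated for discharge.

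**Who can be rescued.** Under Protocol 6.2.1, artesunate patients receive no other IV antimalarial as rescue. Cipargamin patients may receive IV artesunate, for example for clearance below 90% at 24 h or for clinical decline. Under Protocol 6.1.4, cipargamin patients who need longer IV treatment move to IV artesunate, and SAP 2.4.2 classes investigator-chosen IV artesunate in that arm as rescue.

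**Protocol rule.** For parasite and fever clearance, Protocol 12.5.1 says that, without an event, "the time to the event will be censored at the last relevant assessment". It does not mention rescue. SAP Section 4, "Change to protocol specified analyses", reads None.

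**The concern.** In a recovery-time endpoint, death and failure of the randomised drug should not look like fast recovery.

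In the descriptive discharge summary, an early death is given a value lower than any survivor can reach, and the patient is counted among those discharged on that day. In the time-to-discharge and time-to-oral-therapy analyses, death is censored. This treats the dead as if they would have gone on to recover at the same rate as the others.

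The rescue rule removes cipargamin patients from the risk set partly because they clear slowly or deteriorate, while equally slow artesunate patients stay in. Time to oral therapy shows this most plainly. The first permitted switch is at 48 h, so a cipargamin patient rescued at 24 h leaves before any event can occur. An artesunate patient who needs prolonged IV treatment remains at risk until the switch.

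The SAP reports stratified log-rank tests and 90% intervals for hazard ratios on these endpoints, and parasite clearance time is an output for the interim assessment after Cohort 2 (SAP Table 2-13). Readers will take those hazard ratios as evidence of speed.

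**Working it through.** **Figures in the plan.** No figure is given for these rules. The nearest is the study-wide count of 14 of 116, which is also the rescue trigger. The binomial tail P(at least 14 of 116) is 0.845 at a true rate of 15% and 0.160 at 9%, which agrees with the stated above 80% and below 20%. The cohort split is 6 + 14 + 38 + 38 + 20 = 116. Staying one below each cohort trigger (2, 2, 6, 6, 3) allows 1 + 1 + 5 + 5 + 2 = 14 rescues, and the study-wide trigger caps this at 13, or 13/116 = 11.2%. A rescue share of about 10% is therefore possible without a pause.

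**Discharge day.** Assumptions, not in the documents: survivors leave on Day 4/5/6/7/8 in 60/20/10/5/5%, a mean of 4.75; deaths fall on Days 1 to 3.

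Mean under the plan = [(116 − d) × 4.75 + d × day of death] / 116.

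- 12 deaths (10.3%) on Day 2: (104 × 4.75 + 12 × 2)/116 = 518/116 = 4.47, a shift of −0.28 day. For deaths on Day 3 to Day 1 the shift is −0.18 to −0.39.
- 6 deaths (5.2%): −0.09 to −0.19 day.
- Worst value (Day 29) instead, 12 deaths: (494 + 348)/116 = 7.26, a shift of +2.51 days.
- Share out by Day 4 with 12 deaths: (0.6 × 104 + 12)/116 = 64.1% under the plan. Truly discharged alive: 62.4/116 = 53.8%. With deaths censored: 60.0%.

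**Rescue censoring with no true difference.** Assumptions: 116 per arm; the same log-normal clearance time in both arms (log-SD 0.5), read at the smear times of Table 8-1 up to 168 h; a share of cipargamin patients rescued at 24 h and censored there if not yet clear; a stated correlation between rescue risk and slow clearance. The hazard ratio is exp((O − E)/V) from an unstratified log-rank test; above 1 means cipargamin looks faster. A false positive is significance for faster at one-sided 5%.

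| Median, both arms | Rescued | Correlation | Hazard ratio | False faster |
|---|---|---|---|---|
| 30–42 h | 10% | 0.5–0.9 | 1.09–1.27 | 12–38% |
| 30–42 h | 3% | 0.5–0.9 | 1.02–1.07 | not tabulated |
| 18 h | 10% | 0–0.9 | at most 1.14 | at most 17% |
| 15 h | 10% | 0–0.9 | at most 1.08 | at most 10% |
| 12 h | 10% | 0–0.9 | 0.99–1.02 | 5–6% |

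The upper end of the first row is the least stable; repeat runs reached about 1.28 and 44%. Without rescue censoring the false-positive rate is 4–6%.

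**Bounding cases** (Cox model, median 40 h, 400 simulated trials). If rescue picks exactly the slowest 3, 6 or 13 cipargamin patients, censoring gives 1.10, 1.19 or 1.41. If rescue is unrelated to clearance speed, censoring gives about 1.00. Counting rescued patients as never cleared gives 0.96, 0.92 or 0.85 in the first case and 0.89, 0.83 or 0.71 in the second.

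**The case against.** The strongest reply is that the consequence is small. SAP 2.7.2 sets no hypotheses for these secondary endpoints. Mortality and in-hospital mortality are tabulated separately (SAP 2.8.1), as is rescue use (SAP 2.4.2 and 2.15.2). The primary endpoint, clinical success at 48 h, and the 90% reduction endpoints at 24 and 48 h all count rescue as failure. This stands, and it sets the severity.

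A reader might infer that all recovery-time endpoints score death as early discharge. They do not. Only the descriptive summary does, and the time-to-discharge analysis censors deaths. The descriptive rule is also the protocol's own, as is censoring at death for time to oral therapy. With equal mortality in the arms the discharge means do not differ. A 3-point difference, with deaths on Day 2, moves the mean by only 0.03 × 2.75 = 0.08 day, and the median, also reported, would barely move.

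A reader might also infer that the hazard ratios favour cipargamin whenever the drugs are equal. That holds only if rescue comes before the event and selects slow patients. Rescue can also follow safety concerns. Protocol 1.1 reports a median clearance below 12 h for oral cipargamin in earlier studies; at that speed few patients are left to censor at 24 h. In reply, the SAP (5.8.4) expects a median above 40 h for artesunate, so cipargamin that is no faster than artesunate is the case in which the bias appears. The rescue rate and the correlation remain assumptions, and only parasite clearance was simulated, not fever clearance or oral switch.

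Finally, one might ask to restore a protocol rule of observed event time regardless of rescue. The protocol states no such rule; it is silent on rescue. That analysis would credit cipargamin with clearance achieved by IV artesunate.

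**Conclusion.** Wrong as written, and it should be fixed, at secondary-endpoint severity. Two statements follow from the text without assumptions. The descriptive discharge summary gives a death on Days 1 to 3 a better value than any survivor can have. Rescue censoring of parasite clearance, fever clearance and time to oral therapy is in practice one-sided, is linked to poor response by the rescue criteria, and is an addition to the protocol that SAP Section 4 does not declare.

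The direction follows: early deaths shorten the apparent stay, and censoring can favour cipargamin. The size does not come from the documents. For discharge it is a few tenths of a day at about 10% early mortality. For parasite clearance it ranges from nothing (median 12 h, or rescue unrelated to clearance) to a hazard ratio of about 1.27 and a 38% false-positive rate (10% rescued, correlation 0.9, median 30–42 h). The documents do not support a claim that the primary or key secondary conclusions are affected.

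**What to change.** - **Day of discharge:** summarise it in survivors with in-hospital deaths shown alongside, or give deaths the worst value. Do not use the day of death.
- **Time to discharge and time to oral therapy:** keep deaths in the risk set to Day 29 as not having reached the event, or report cumulative incidence with death as a competing event.
- **Parasite clearance, fever clearance and time to oral therapy:** count rescue before the event as event not reached, in line with the composite strategy of the primary and 48-hour estimands. Keep the rescue-censored and observed-time versions as sensitivity analyses. The composite measures recovery without rescue. Because only cipargamin can be rescued, it can fall below 1 when clearance is equal, as the bounding cases show, so all three versions should be read together.
- **SAP Section 4:** list each departure from the protocol, including the changed death rules, because the protocol has the day-of-death sentence and the censoring at death for oral therapy.

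The cost is SAP wording, programming and a few sensitivity tables. No new data are needed.
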